monthly for therapy and monitoring. The primary outcome will be a binary indicator of discontinuation success, the percent of patients successfully transitioned off BUP and abstinent from opioids at the end of the trial, 25 weeks after randomization. We hypothesize that success rate will be greater in patients that received treatment with XR-NTX.

Setting and Screening: This study will be conducted at the BSU clinic at NYSPI where we have previously carried out recruitment and treatment of opioid-dependent subjects using similar methodology. A combination of radio, print, and Internet advertising will be directed at prospective participants in the New York metropolitan area. Screening procedures are standardized for clinical trials including a telephone interview, the MINI International Neuropsychiatric Interview, psychiatric evaluation, medical history, physical and laboratory examination. The research psychiatrist will offer eligible individuals participation in the study and will obtain informed consent.

Randomization. We predict that 50 participants (out of 60 enrolled) will complete lead-in phase successfully and will be available for randomization. The 1:1 randomization will be stratified by the BUP maintenance dose (4 mg/d vs. greater than 4 mg/d) and the type of the primary drug (prescription opioids vs. heroin) distributing these potential prognostic factors equally between groups to ensure comparable representation. The randomization sequence will be carried out by a research pharmacist, balanced in random blocks to protect allocation concealment.

Regimen 1 will include a rapid Monday to Friday oral naltrexone-induction procedure: last dose of BUP on Sat, Sun-Mon 0 mg, Tue 1 mg, Wed 3 mg, Thu 6 mg dose of oral NTX respectively. On Friday, a final 25 mg dose of oral NTX will be given followed by an injection of XR-NTX (Vivitrol; 380 mg IM). All doses of oral NTX will be given in a single or split doses depending on patients' tolerability of the protocol. Throughout the induction adjuvant medications will be administered on standing basis: clonidine 0.1 mg qid, clonazepam 0.5 mg qid, and zolpidem 10 mg HS. Additional injections of XR-NTX will be administered 4 and 8 weeks after the first injections to participants who provide an opioid-negative urine or pass a naloxone challenge test.

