Procedures for Missed Doses of Long-acting Naltrexone: Missing a scheduled Vivitrol injection is the most important threat to the success of long-acting naltrexone maintenance. In the event of a patient missing a scheduled injection, the clinic staff will immediately attempt to contact the patient to re-establish commitment to the naltrexone treatment and reschedule the injection within a 48-hour period, or as soon as possible thereafter, based on clinical judgement (i.e., after a clinical assessment and naloxone challenge if indicated). If the patient cannot attend the treatment clinic within that time-frame, or cannot be located, the treatment team will use previously obtained locator information in an effort to locate the patient through emergency contacts and get him/her in for a clinic visit. If opioid use occurs in combination with a missed Vivitrol injection, a naloxone challenge will be administered to confirm that the next long-acting naltrexone injection will be safely tolerated.

Regimen 2 will include a 5-week BUP taper from the maintenance dose of 8, 6, 4, or 2mg (wk 1: 6, 5, 3 2mg/d, wk 2: 4, 4 or 2 mg/d, wk 3: 3, 3 or 2 mgd/, wk 4: 2 mg/d, wk 5: 1 mg/d). A buprenorphine/naloxone generic product will be used. Participants will be offered adjuvant medications, which will be administered on standing basis: clonidine 0.1 mg qid, clonazepam 0.5 mg qid, and zolpidem 10 mg HS. Additional

injections of XR-NTX will be administered 4 and 8 weeks after the first injections to participants who provide an opioid-negative urine or pass a naloxone challenge test.

Participants in both regimens will be seen in the clinic for 25 weeks for follow-up after randomization, which will include both the week induction onto Vivitrol in Regimen 1 and the 5 week buprenorphine taper in Regimen 2.

We will collect 4ml of saliva, 50ml of urine, and 4, 6-7ml blood from subjects at baseline, after randomization (3 weeks after 1st injection of XR-NTX, or 1 week after completing bup taper), during post randomization month 2 (1 week after 2nd XR-NTX injection, or 4 weeks after completion of bup taper), and at end of study to be examined for biomarkers. From these we will isolate extracellular vesicle-containing pellets and evaluate their contents using advanced -OMICs analyses, in order to identify molecular signatures that differ across subjects before and after ending treatment with buprenorphine.

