Urine samples will be collected at every visit, and we will use onsite testing to provide immediate feedback on opiate use to the participant and the treatment team. Blood chemistry will be obtained at baseline and end of study (week 25). Urine Pregnancy tests will be obtained at baseline, at once monthly (or prior to administration of XR-NTX).

We will collect 4ml of saliva, 50ml of urine, and 4, 6-7ml blood from subjects at Baseline, after randomization (3 weeks after 1st injection of XR-NTX, or 1 week after completing bup taper), during post randomization month 2 (1 week after 2nd XR-NTX injection, or 4 weeks after completion of bup taper), and at end of study to be examined for biomarkers. From these we will isolate extracellular vesicle-containing pellets and evaluate their contents using advanced -OMICs analyses, in order to identify molecular signatures that differ across subjects before and after ending treatment with buprenorphine.

Assessment Instruments

Create a table or give a brief description of the instruments that will be used for assessment

Physiological Measures

Medical History and Physical Exam: A comprehensive medical history and physical examination will be performed during the screening process. All potential participants will be offered the opportunity to be referred to receive free HIV risk reduction education, as well as HIV testing and counseling.

Pregnancy Testing: Serum pregnancy testing will be performed on all females during screening and urine pregnancy tests will be performed at baseline and monthly afterwards.

Serum laboratory examination: Complete blood count, electrolyte, and liver function tests will be performed during the screening process and at the end of study.

Urinalysis: Laboratory urinalysis (glucose, protein, ketones, pH, specific gravity, and microscopic analysis) will be performed during the screening process and at the end of study.

Urine Toxicology: Urine samples will be collected under directly--observed conditions during screening and at each study visit. To provide immediate feedback to the participant, the Abuscreen On--Trak system (Roche Diagnostics) will be used to identify opiates (morphine, oxycodone, buprenorphine, methadone). In addition, the sample will be analyzed for substances of abuse, including THC, alcohol, opioids, cocaine, benzodiazepines, amphetamines, and barbiturates.

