Spielberger State--Trait Anxiety Test (SSTAT)-- Self: The SSTAT is a well--validated measure of anxiety consisting of two self--rated subscales, one rating Trait anxiety and the other State anxiety (Spielberger et al., 1970).

Beck Depression Inventory (BDI)-- Self: The BDI is a 21--item self--report questionnaire. It has been used in many studies and validly and reliably assesses depression in many patient groups including substance abusers (Beck et al., 1996) and it will be collected weekly, **and twice-monthly during study months 4-6.**

Subjective Opiate Withdrawal Scale (SOWS)-- Self: The SOWS is a 19--item self--report scale reliably eliciting severity of common physical and mental symptoms of opiate withdrawal, and also yielding a total withdrawal severity score (Handelsman et al., 1987). It will be used to examine occurrence of symptoms resembling opiate withdrawal during naltrexone maintenance and will be collected at each visit.

Locator Form-- Self: In order to facilitate the location of drop--outs for follow--up evaluation, a standard location form will be administered at baseline and updated monthly. This indicates names, addresses and phone numbers of family members and close friends likely to know patients' whereabouts along with permission to contact them in the future.

Please attach copies, unless standard instruments are used

Off label and investigational use of drugs/devices

Choose from the following that will be applicable to your study

Research Related Delay to Treatment

Will research procedures result in a delay to treatment?

Yes

Maximum duration of delay to any treatment

A delay of up to 2 weeks is possible prior to enrollment.

Maximum duration of delay to standard care or treatment of known efficacy

Up to two weeks.

Treatment to be provided at the end of the study

Discharge and aftercare planning and implementation will be incorporated into the study. A Discharge Plan will be completed by a clinician and approved by a study physician prior to the End of Study visit. After the End of Study, participants will continue in a follow-up phase with once weekly clinic visits with their therapist for up to one month in order to facilitate transition and permit overlap with another treatment program for aftercare. Discussion of treatment recommendations as well as risks and benefits of accepting and refusing referrals will take place and will be documented.

**New York State
Psychiatric Institute**
INSTITUTIONAL REVIEW BOARD

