The most common side effect associated with injectable naltrexone is injection site reaction. XR-naltrexone is administered as a gluteal intramuscular injection and injection site reactions, mostly pain, and occur in approximately 5% of patients in opioid treatment studies. These reactions are generally mild and include pain, tenderness, indurations, bruising, pruritus and swelling. Generally these reactions last 1--3 days. Rare skin reactions at the site of the injection have been reported, including sterile abscesses, which may relate to inadvertent injection into fatty tissue, rather than muscle. Patients will be informed of this risk, and baseline physical evaluation will include examination of the buttock for excessive adiposity. If a patient is examined by a physician and found to have an abscess, necrosis, cellulitis or extensive swelling, an appropriate surgical referral will be made.

Naltrexone has been associated with reversible hepatocellular injury indicated by elevated liver enzymes when administered at doses substantially greater than the 380 mg im per month, dose recommended for relapse prevention treatment of opiate dependence and proposed for the present study. When used in therecommended dose range in opiate--dependent patients, this risk is remote (Brahén et al., 1988;; Brewer and Wong, 2004). Naltrexone is therefore contraindicated in patients with acute hepatitis or liver failure, and such patients are excluded from the study. Patients with hepatic enzyme levels greater than three times the upper limit of normal are excluded. Injectable naltrexone achieves higher blood levels than oral naltrexone initially, but these should remain lower than levels associated with hepatitis. If naltrexone--induced hepatitis were to occur in the setting of long--acting preparation, where the naltrexone would be only very slowly eliminated, this would prolong exposure to the offending agent. However, the experience with injectable naltrexone also suggests it is safe. In our studies with extended--release naltrexone several patients experienced elevation in liver enzymes, which were determined to be related to hepatitis C. In the proposed study we will use a long--acting, injectable preparation of naltrexone (Vivitrol 380 mg).

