All data will be obtained specifically for research purposes. Data will be entered and maintained in the clinical trials electronic database coded with a unique identifier assigned to each participant. Departmental, HIPPA-compliant Research Subject Registration System, will however contain participants' names.

C2. Data Entry Methods

Data collection will be achieved using a structured, integrated, network-based computerized system. Specifically, data management will include: 1) protocol management; 2) patient scheduling; 3) regulatory reporting and 4) management of research organizations, personnel, and collaborators. The research staff will collect and input data on a daily, basis to reduce the likelihood of errors. Information collection and analysis and study-specific data collection will be easily retrievable, organized, and reviewed on an ongoing basis as well.

Table 1. List and Schedule of Assessments Carried out During the Treatment Trial

	Screen	Base- line	BUP Stabiliza- tion/Taper (weekly)	NTX Induction (Daily)	Relapse Prevention (weekly)	End of study (week 25)
Medical assessments						
Blood chemistry, hematology, hepatitis panel, thyroid panel, urinalysis, ECG, physical exam	X					X
Vital Signs	X	X	X	X	X	X
Pregnancy Test	X	X	q month		q month	
Urine Toxicology	X	X	X	X	X	X
ETOH Breathalyzer	X	X	X	X	X	X
Medication Form		X	X	X	X	X
Time Line Follow Back		X	X	X	X	X
Participant						
Clinical Global Impress Scale - Self		X	X		X	X
Craving Scale		X	X	X	X	X
Spielberger State-Trait Anxiety Test		X	X		X	X
Beck Depression Inventory		X	X		X	X
Subjective Opiate Withdrawal Scale		X	X	X	X	X
Medical Outcomes Study Sleep S. Locator Form	X	X	X	X	X	X
Investigator/Therapist					q month	
MINI Interview for DSM-5	X					
Therapist Contact Log			X		X	
Investigator/Psychiatrist						
Systematic Assessment for Treatment Emergent Effects			X		X	X
Hamilton Depression Scale		X	X		X	X
Hamilton Anxiety Scale		X	X		X	X
Global Impression Scale -Observer		X	X		X	X
Treatment Service Review			X		X	X
End of Study Form						X

C3. Data Analysis Plan

Study Aim #1: To estimate the difference in the rate of successful transition off BUP at 25 weeks post randomization between the group that received naltrexone post-buprenorphine and the one that did not. We hypothesize that more patients will be transitioned off BUP and stable at the end of trial in the group that received XR-NTX.

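### No liver test is scheduled during XR-NTX exposure: the only one after treatment starts is at week 25, about 16 weeks after the third injection, so scheduled testing would miss a silent, transient enzyme rise.

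*Protocol*

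**What the plan says.** **Liver tests.** Under Assessment Instruments (Serum laboratory examination) the Protocol states: "Complete blood count, electrolyte, and liver function tests will be performed during the screening process and at the end of study". Under Blood and other Biological Samples it states: "Blood chemistry will be obtained at baseline and end of study (week 25"). In SAP Table 1 the row "Blood chemistry, hematology, hepatitis panel, thyroid panel, urinalysis, ECG, physical exam" is marked at screening and at week 25, and nowhere in the stabilization/taper, induction or relapse-prevention columns. One place says screening and another says baseline, but both precede treatment.

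**Injections.** Protocol, Study Procedures, gives a total of three. The first comes at the end of induction week: "On Friday, a final 25 mg dose of oral NTX will be given followed by an injection of XR-NTX". The second and third follow 4 and 8 weeks later. The 25-week clock starts at randomisation, "which will include both the week induction onto Vivitrol in Regimen 1 and the 5 week buprenorphine taper in Regimen 2". The SAP's opening trial description also gives three monthly injections, but its regimen text then offers additional injections to interested, adherent patients and states no maximum there.

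**Hepatic risk.** Both documents say: "Naltrexone has been associated with reversible hepatocellular injury indicated by elevated liver enzymes". The same sentence ties this to doses well above 380 mg per month, and the next calls the risk remote in the recommended range. Enzyme rises in the group's earlier XR-NTX studies are attributed to hepatitis C. The documents add that, if hepatitis did occur, slow elimination of the depot would prolong exposure.

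**Other blood draws.** Biomarker blood is taken in both arms at two post-randomisation points. The first is "3 weeks after 1st injection of XR-NTX, or 1 week after completing bup taper". The second is 1 week after the second injection, or 4 weeks after the taper ends.

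**The concern.** SAP A4 names safety, with feasibility, tolerability and acceptability, as the primary aim of the pilot, and SAP A2 lists adverse events as a secondary outcome. The documents describe a possible liver effect of naltrexone as reversible, and screen for enzymes above 3 times the upper limit of normal (ULN) at entry. Yet no liver value is scheduled between the first injection and week 25.

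Hepatitis C as such is not a listed exclusion. Patients like those whose enzymes rose in the earlier studies could therefore be enrolled, provided they met the entry limit and did not have acute hepatitis or liver failure. With no value taken during exposure, scheduled testing could not show whether such rises recur, when they occur, or whether they differ by arm. At stake is the completeness of the safety description passed on to a larger trial.

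**Working it through.** The plan states no figure for the gap between last injection and liver test, so there is none to reproduce. The gap follows from the calendar.

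**Inputs.** First injection on the Friday of induction week; second and third 4 and 8 weeks later; induction counted within the 25 weeks; final chemistry at week 25 (all Protocol); 25 patients per arm (SAP A4).

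**Injection days**, taking Monday of induction week as day 0:
- Injection 1: day 4
- Injection 2: 4 + 28 = day 32
- Injection 3: 4 + 56 = day 60
- End of the last 4-week interval: 60 + 28 = day 88
- Week 25: 25 × 7 = day 175

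**Gap to the final liver test:**
- From injection 3: 175 − 60 = 115 days = 16.4 weeks
- From the end of its interval: 175 − 88 = 87 days = 12.4 weeks

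**Range.** The visit may fall 24 to 25 weeks after the clock starts, and the first injection 0 to 1 week after it starts. The gap from injection 3 then runs from 24 − (1 + 8) = 15 to 25 − (0 + 8) = 17 weeks. Subtracting 4 gives 11 to 13 weeks after the last interval.

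**Other numbers of injections.** With the first at week 1, n injections leave a gap of 25 − [1 + 4(n − 1)] weeks:

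| Injections | 1 | 2 | 3 | 4 | 5 | 6 | 7 |
|---|---|---|---|---|---|---|---|
| Weeks to the week-25 test | 24 | 20 | 16 | 12 | 8 | 4 | 0 |

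The columns beyond 3 apply only if the SAP's additional-injection offer is read as extending the course. In every column, no liver test is scheduled after the first injection until week 25.

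**Where the existing draws fall:**
- XR-NTX arm: 4 + 21 = day 25, and 32 + 7 = day 39. Both are within exposure.
- Taper arm: weeks 5 + 1 = 6 and 5 + 4 = 9.

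**What values at those draws could show.** Assume all 25 XR-NTX patients are sampled and any rise is present at sampling. The chance of seeing at least one is 1 − (1 − p)^25:

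| Assumed true rate p | 1% | 2% | 5% | 10% |
|---|---|---|---|---|
| Chance of at least one | 22% | 40% | 72% | 93% |

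Seeing none in 25 would leave a one-sided 95% upper bound of 1 − 0.05^(1/25) = 11.3%. The rates are illustrative; the documents give none.

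**The case against.** The strongest reply is that the plan gives a reason for light monitoring. It links the reversible injury to doses well above the trial dose, calls the risk at the recommended dose remote, attributes the group's earlier rises to hepatitis C, and cites recent reports of lower hepatotoxicity and removal of the boxed warning. Protocol and SAP agree on the schedule, and there is no hepatic endpoint. All of this stands, and it keeps the point modest.

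Other routes to detection also exist. Physician review and SAFTEE are weekly through the injection months, and SAP E1 counts laboratory findings as adverse events. These could bring a symptomatic case to light. They would not find a silent rise, because no liver result is scheduled to feed them.

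A reader might infer that the plan is unable to detect liver injury at all, or that any effect would be gone by week 25. The documents support neither. They give no recovery time and describe slow elimination of the depot, so a lasting rise could still appear in the final sample.

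Two objections to the remedy also stand. Nothing is drawn between day 39 and week 25, so the period after injection 3 stays unsampled. The draws are not time-matched between arms. In addition, the biomarker blood is allocated to vesicle work with no spare volume stated, so an extra tube may be needed.

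**Conclusion.** The point holds as a modest gap in safety data collection. On the three-injection course, the only liver test after treatment starts falls about 16 weeks (15 to 17) after the last injection and about 12 weeks (11 to 13) after its interval ends. No scheduled liver value is obtained during exposure. Scheduled testing would miss an asymptomatic rise that resolves before week 25; it would not necessarily miss a lasting one.

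The 16 weeks rests on exactly three injections given on schedule, with induction starting at randomisation. If further injections are allowed, the final gap shortens, but exposure lengthens and still has no scheduled test before week 25. The case for acting rests on the stated safety aim, the absence of hepatitis C from the listed exclusions, and the low cost, since blood is already drawn twice during exposure. It does not rest on a high expected hepatic risk.

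**What to change.** 1. Add AST and ALT, in both arms, at the two post-randomisation biomarker draws (about days 25 and 39 in the XR-NTX arm, about weeks 6 and 9 in the taper arm), with an extra tube if needed.
2. Enter these points in the Protocol (Blood and other Biological Samples; Serum laboratory examination) and in SAP Table 1, which has no biomarker row at present.
3. In the SAP, report AST and ALT as multiples of ULN by arm and visit, beside the week-25 value.
4. State the limits there: the period after injection 3 is unsampled, so the values are not a full on-treatment maximum, and the arms are sampled at different times.
5. Reconcile the SAP's offer of additional injections with the total of three in the Protocol and in the SAP's own trial description.

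The change concerns assessment and reporting only. It costs about 50 × 2 = 100 samples for routine assay and some incidental abnormal results to follow up, with no new visit or venepuncture.

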Contingency Management and Subject Compensation: Subjects will be encouraged to come for the clinical evaluations and for CBT sessions as described in this protocol. To minimize missed sessions, they will be reimbursed for transportation expenses, for providing data, and for time spent in completing study assessments in accordance with local site's IRB policies. Contingency management procedures which have been shown to successfully improve many behaviors ranging from medication compliance to adherence to protocol activities will be applied to this study. Subjects will earn chances at each visit to draw vouchers from a prize-bowl. A subject must complete all visit requirements to be able to draw vouchers at the end of a visit. If study medication is discontinued due to adverse events, subject will continue to draw vouchers based on the schedule below as long as they continue all other visit requirements are completed. Participants will earn one draw for each consecutive visit made, with a bonus 3 draws for every 3 consecutive weeks. If a participant misses a visit, their draws are reset. Each draw has a probabilistic chance of yielding one of four outcomes; an encouraging statement (e.g. 'good job'), a small prize valued at \$2.50, a large prize valued at \$20, or a jumbo prize valued at \$100. The probability of each particular outcome is fixed for every draw and is based on the relative number of slips for each prize category in the prize bowl. Using Petry et al.s (2005) framework each prize bowl will have 500 prize slips. 250 slips will be an encouraging statement (50% of the total slips), 209 will be for small prizes (41.8%), 40 slips will be for large prizes (8%), and 10 slips will be the jumbo prize (0.2%). Patients will earn 1 additional draw for every consecutive week of abstinence (all urine samples for a treatment week test negative). The increasing number of earned draws during the protocol follows the escalating incentive structure employed in other CM based treatments (Higgins et al., 1993). During the treatment (contingency management) subjects can earn up to **340** draws from the prize bowl if demonstrating 100% attendance during the 25 weeks of the protocol. Total earnings will vary depending on attendance. With an expected earning of \$2.85 per draw the maximum potential earnings for the CM for 25 weeks is **\$969**. However, actual observed earnings will be significantly less than the potential maximum due to attrition and missed visits.

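### The prize bowl's printed count of 10 jumbo slips contradicts its own 0.2%, the 500-slip total, and the $2.85 and $969 figures, all of which fit 1 jumbo slip

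*Protocol*

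**What the plan says.** The prize schedule is in the protocol under Compensation and/or Reimbursement, in the paragraph on contingency management and subject compensation. It fixes the size of the bowl: "each prize bowl will have 500 prize slips". It then lists the contents:

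- no-prize slips: "250 slips will be an encouraging statement (50% of the total slips");
- small prizes: "209 will be for small prizes (41.8"%);
- large and jumbo prizes: "40 slips will be for large prizes (8%), and 10 slips will be the jumbo prize (0.2"%).

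The prize values are "a small prize valued at \$2.50", "a large prize valued at \$20, or a jumbo prize valued at \$100". The link between counts and odds is explicit: "The probability of each particular outcome is fixed for every draw and is based on the relative number of slips" in each prize category.

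The paragraph then gives an expected $2.85 per draw and up to 340 draws with full attendance. It says that "the maximum potential earnings for the CM for 25 weeks is" $969. It adds that actual earnings will be lower because of attrition and missed visits.

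The SAP gives no prize-bowl figures. In section F1 (Other Risks) it recognises that compensation and incentives could give participants money to buy illicit opioids. In section F3 (Procedures to Minimize Other Risks) its answer is to keep the amounts low.

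**The concern.** The jumbo count cannot be reconciled with the percentage printed beside it, or with the stated size of the bowl. Because the jumbo prize is worth $100, a tenfold difference in that one count changes the expected payout substantially.

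The count is also the figure that staff would use: a bowl is filled by counting slips, and the text makes the odds depend on those counts. If the bowl is filled as printed, participants are paid more than the protocol says, and the SAP's safeguard of modest payments is weaker than described.

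Only the compensation plan is at stake. The protocol describes one prize schedule for all subjects and makes no distinction by arm, so no effect on the randomised comparison is claimed.

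**Working it through.** **Inputs** (all from the protocol's compensation paragraph): bowl of 500; counts 250 / 209 / 40 / 10; percentages 50 / 41.8 / 8 / 0.2; values $0 / $2.50 / $20 / $100; 340 draws; $2.85 per draw; $969.

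**Formula.** Expected value per draw = sum of (slips × value) ÷ total slips. Expected earnings = 340 × that value.

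**1. The plan's own figures, from its percentages.** 50 + 41.8 + 8 + 0.2 = 100.0%. Expected value = 0.418 × 2.50 + 0.08 × 20 + 0.002 × 100 = $2.845, which rounds to $2.85. Then 340 × 2.85 = $969 exactly (unrounded, 340 × 2.845 = $967.30). The stated dollar figures reproduce.

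**2. The printed counts.** 250 + 209 + 40 + 10 = 509, not 500. Jumbo share: 10/500 = 2.0%, or 10/509 = 1.96%; neither is 0.2%.

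**3. One jumbo slip.** 250 + 209 + 40 + 1 = 500, and 1/500 = 0.2%. Prize money in the bowl: 209 × 2.50 + 40 × 20 + 1 × 100 = $1,422.50. Divided by 500, this is $2.845. Everything agrees.

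**4. Ten jumbo slips.** Prize money in the bowl: 522.50 + 800 + 1,000 = $2,322.50.

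| Bowl | Slips | Expected value per draw | 340 draws | Above $969 |
|---|---|---|---|---|
| 1 jumbo slip | 500 | $2.845 | $967 ($969 using $2.85) | none |
| As printed, 10 jumbo | 509 | $4.563 | $1,551 | 60% |
| 10 jumbo, 9 fewer no-prize slips | 500 | $4.645 | $1,579 | 63% |
| 10 jumbo, 9 fewer small-prize slips | 500 | $4.60 | $1,564 | 61% |
| 10 jumbo, 9 fewer large-prize slips | 500 | $4.285 | $1,457 | 50% |

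No arrangement tried with 10 jumbo slips gives $2.85. For the bowl as printed, the gap is 1,551 − 969 = $582. Expected jumbo prizes over 340 draws are 340 × 10/509 = 6.7, against 340 × 0.002 = 0.7.

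**5. Is $969 a maximum?** It is a mean multiplied by the maximum number of draws. Taking draws as independent with fixed odds, the mean squared prize with 1 jumbo slip is (209 × 6.25 + 40 × 400 + 10,000)/500 = 54.61. The SD over 340 draws is then √[340 × (54.61 − 2.845²)] ≈ $126. With the printed counts it is √[340 × (230.46 − 4.563²)] ≈ $267. A participant who earns every draw can therefore exceed $969 by chance, however the bowl is filled.

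**The case against.** The strongest reply is that this is a one-character slip which the paragraph all but corrects itself. The 0.2% stands beside the 10, the total of 500 is stated just before, the other three counts match their percentages, and the dollar figures fit 1 slip. Overpayment requires someone to fill the bowl with 10 jumbo slips despite all of that. The dollar gap also assumes all 340 draws, and the protocol itself expects actual earnings well below that level.

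Much of this stands. The intended figure is hardly in doubt, and the overpayment is hypothetical. The $582 gap applies only at full attendance, and the 340 is taken as stated and was not rederived. The 60% difference per draw does not depend on it.

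What the reply does not remove is the error itself. The count is the figure used to fill the bowl, and nothing elsewhere in the protocol or SAP corrects it.

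On the label for $969, it is fair that the paragraph shows its derivation from an expected value and calls the draws probabilistic. Calling the result a maximum is still inaccurate, though this is a secondary point.

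**Conclusion.** The concern holds: the count of 10 jumbo slips is wrong as written. That conclusion is arithmetic on the protocol's own numbers and needs no outside assumption beyond rounding $2.845 to $2.85. The stated $2.85 and $969 are sound for a bowl with 1 jumbo slip.

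The consequence is conditional. If the bowl holds 10 jumbo slips, expected payment per draw is 60% above the stated value for the printed 509 slips. It is 50% to 63% above if another category is cut to keep 500. Equivalently, the stated figures would be 37.5% too low for the printed bowl (1 − 2.85/4.563). The documents do not show which bowl was used, and the consent form is not among them, so what participants were told cannot be checked here.

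This should be corrected, but it reaches no further than the compensation plan.

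**What to change.** Change the jumbo count from 10 slips to 1. The counts then sum to 500, and $2.85 and $969 stay as they are. Confirm how the physical bowl is, or was, filled.

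If 10 jumbo slips are actually used, restate the total, the percentages, the expected value per draw and the expected earnings at 340 draws, both in the protocol and wherever participants are told about payment.

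In either case, describe the resulting figure as expected earnings at the maximum number of draws.

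The cost is one number, one change of wording and one count of the slips in the bowl. Nothing in the statistical analysis changes.
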